### 8.7 STUDY STOPPING RULES

The overall study will be paused, and appropriate authorities (e.g., IRB, Knight Data and Safety Monitoring Committee) notified if the following events occur:

- Life-threatening grade 4 toxicity attributable to protocol therapy that is unmanageable, or unexpected
- Death suspected to be related to SBRT

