##### **4.3.1 ACCRUAL ESTIMATES**

The number of participants to be accrued is driven by the study primary objective. An estimated 15 participants over a 12 month period.

This study will not focus on any particular gender, racial or ethnic subset. No participant will be excluded from the study on the basis of gender, racial or ethnic origin. Gender-nonconforming and gender-fluid individuals as members of the general population will also be recruited. Male, female and minority volunteers will be recruited for this study from the general population. The incidence of male HCC is disproportionately higher than females; at a rate of approximately 2:1 across studies reported. The projected gender, racial, and ethnic composition of the study, adjusted for the approximate 2:1 disproportion in male to females, will otherwise represent that of the state of Oregon (**Table 1**).

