##### 6.1.6.1 Radiation-induced liver toxicity

Radiation-induced liver disease (RILD) is defined as either classical or non-classical RILD. Classical RILD (typically occurring in patients without background liver dysfunction or cirrhosis) is characterized as the presence of nonmalignant ascites and anicteric elevation of alkaline phosphatase level twice the upper level of normal or baseline value occurring between 2 weeks and 3 months after the completion of irradiation. Non-classical RILD (typically occurring in patients with baseline liver dysfunction or cirrhosis), occurs is defined as grade 4 AST and/or ALT elevations, or an increase in CP score of  $\geq 2$  within 1 week to 3 months after completing SBRT.

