### 8.3 EXPECTEDNESS

The investigator will be responsible for determining whether an AE is expected or unexpected. An AE will be considered unexpected if the nature, severity, or frequency of the event is not consistent with the risk information previously described for the study agent.

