## **8.4 ADVERSE EVENT LIST(S)**

### **8.4.1 ADVERSE EVENT LIST FOR SBRT**

Rates of non-classical RILD (defined as a CP elevation of 2 or more within 3 months after radiation) are reported to be in the range of 20-30%.

Rates of Grade CTCAE 1-2 toxicities are reported to range from 0-27% and Grade 3-4 toxicities are observed in around 5%. The most commonly reported toxicities are fatigue, right upper quadrant pain, low-grade pyrexia, and elevation in transaminase. Minor pain, fever and chills (Grade 1) is observed in 14% of patients. Gastric ulceration and esophagitis occurred at rates of 7% (Grade 2) and 3% (Grade 3), respectively.

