## 10. CLINICAL MONITORING

## 10.1 OHSU KNIGHT CANCER INSTITUTE DATA & SAFETY MONITORING PLAN

This study is under the oversight of the Knight Cancer Institute's DSMC as described in the Knight institutional DSMP. The Knight DSMP outlines the elements required to ensure the safety of clinical trial participants, the accuracy and integrity of the data and the appropriate modification of cancer-related clinical trials for which significant benefits or risks have been discovered or when the clinical trial cannot be successfully concluded. The Knight DSMP also describes the methods and procedures for ensuring adequate oversight of cancer-related research at OHSU.

As described in the Knight DSMP, regardless of a trial's risk level and any specific Knight oversight in place, the Investigator is singularly responsible for overseeing every aspect of the design, conduct, and final analysis of his/her investigation.

The Knight DSMC will review and monitor study progress, toxicity, safety and other data from this study. Information that raises any questions about participant safety or protocol performance will be addressed by the Investigator, statistician and study team. Should any major concerns arise, the Knight DSMC may recommend corrective action and determine whether or not to suspend the study.

The Knight DSMC will review each protocol every 6 months, but may occur more often, if required, to review toxicity and accrual data (please refer to Knight DSMP for additional details on audit frequency). The Knight DSMC will review accrual, toxicity, response and reporting information. Information to be provided to the DSMC may include: participant accrual; treatment regimen information; AEs and SAEs reported by category; summary of any deaths on study; audit results; and a summary provided by the study team. Other information (e.g. scans, laboratory values) will be provided upon request.

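### The pause rule in 8.7 has no RILD count or rate criterion, so Child-Pugh-defined RILD does not by itself pause accrual however often it occurs

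*Combined protocol and SAP*

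**What the plan says.** Section 8.7 has two triggers. The first is "Life-threatening grade 4 toxicity attributable to protocol therapy that is unmanageable, or unexpected". The second is "Death suspected to be related to SBRT". Neither refers to RILD, to the Child-Pugh score, or to a number or proportion of participants.

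Non-classical RILD is a secondary endpoint (3.2.2) and is to be estimated with an exact interval in the safety set (9.2.3). Section 6.1.6.1 gives it two limbs: "grade 4 AST and/or ALT elevations, or an increase in CP score of" 2 or more, "within 1 week to 3 months after completing SBRT". Section 8.4.1 describes it by the Child-Pugh limb only and says that its rates "are reported to be in the range of 20-30" percent.

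Oversight beyond 8.7 is general. Section 10.1 says that the DSMC "will review each protocol every 6 months, but may occur more often, if required, to review toxicity and accrual data", and that it may suspend the study. Section 4.8 includes the frequency or seriousness of adverse events among the grounds for suspending or ending the study. Neither section says how many events would prompt action. On accrual, 4.3.1 gives "An estimated 15 participants over a 12 month period".

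**The concern.** Section 1.4.1 names RILD and loss of liver function as the risk of SBRT. It cites a 31% figure at this institution for a Child-Pugh rise of 2 or more within 6 months. It also cites 7 of 13 patients with Child-Pugh B7 cirrhosis elsewhere who had such a rise within 3 months. This trial enrols B8 or worse, so a rate above the 20-30% in 8.4.1 is plausible on the protocol's own evidence.

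The pause rule looks elsewhere. It responds to single extreme events that someone attributes to SBRT, while 1.4.1 concedes that treatment toxicity is hard to separate from the natural course of cirrhosis. An excess of moderate decompensation across participants, which shows as a count and not as one alarming case, has no pre-stated consequence. These are transplant candidates with little hepatic reserve, so when such an excess is acted on matters to those not yet treated.

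**Working it through.** **The plan's own figure.** The documents give no operating characteristic for the pause rule. Their only computed design figure is N = 15 in 9.3.1, for seeing at least one SBRT-ineligible patient at a 20% rate. That reproduces approximately: 1 − 0.8^15 = 96.5%, and 14 would already give 95.6%. It has no bearing on RILD monitoring.

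**Does Child-Pugh RILD reach 8.7?** The first trigger needs a grade 4, life-threatening, attributable event that is also unmanageable or unexpected. A Child-Pugh rise of 2 need not be grade 4. Section 8.3 says "An AE will be considered unexpected if the nature, severity, or frequency of the event is not consistent with the risk information previously described", so an excess frequency could make RILD unexpected, but the grade 4 condition still has to be met. Over 15 participants the expected number of cases is 15 × 0.20 = 3.0 to 15 × 0.30 = 4.5 at the listed rates, and 15 × 0.50 = 7.5 at a true 50%. In either situation, Child-Pugh rises without a qualifying grade 4 event or suspected related death leave 8.7 untouched.

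**What a month-6 review would see.** Inputs: 15 participants in 12 months (4.3.1), so 15/12 = 1.25 per month or one every 0.8 month; SBRT lasting about 10 days, 0.33 month (Synopsis), or two weeks (5.2); window closing 3 months after SBRT (6.1.6.1). Assumptions: uniform accrual, and a DSMC clock that starts with the first participant.

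- Started: 1.25 × 6 = 7.5.
- Window complete: 1.25 × (6 − 0.33 − 3) = 3.3.
- With 14 days of SBRT: 1.25 × (6 − 0.46 − 3) = 3.2.
- With a further 28-day screening lag (0.92 month): 2.0 to 2.2.
- With 12 treated in place of 15: 1.0 × 2.67 = 2.7.
- With discrete starts every 0.8 month: 3 or 4.

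The range is about 2 to 4. With three complete windows, the chance of at least one case is 1 − 0.8³ = 49% at a true 20% and 1 − 0.7³ = 66% at 30%. The exact 95% interval is 0-71% for 0 of 3 and 0.8-91% for 1 of 3.

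**A worked count rule.** Reference rate 30% (top of the 8.4.1 range), prior Beta(0.6, 1.4) with mean 0.6/2.0 = 30%, trigger when the posterior probability that the rate exceeds 30% is above 0.95. For example, 3 of 3 gives Beta(3.6, 1.4) and a probability of 0.976, which triggers; 2 of 3 gives 0.838, which does not.

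| Participants evaluated | Cases that trigger |
|---|---|
| 3 | 3 |
| 4-5 | 4 |
| 6-8 | 5 |
| 9-10 | 6 |
| 11-12 | 7 |
| 13-15 | 8 |

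With starts every 0.8 month, the 15th start falls at 14 × 0.8 = month 11.2. Windows complete by then belong to starts no later than 11.2 − 3.33 = 7.87, which is 10 participants. Applying the boundary after each of those 10 gives:

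| True RILD rate | Triggers before the 15th start |
|---|---|
| 20% | 2% |
| 30% | 9% |
| 40% | 24% |
| 50% | 46% |
| 60% | 70% |
| 70% | 88% |

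Random uniform starts give slightly less: 2, 8, 43, 66 and 85% at 20, 30, 50, 60 and 70%.

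**The case against.** A reader might infer three stronger things, and the documents support none of them.

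- *RILD can never trigger 8.7.* It can. The AST/ALT limb is a grade 4 event, and 8.4.1 lists transaminase elevation without a specific grade, so whether that limb is expected is open. Components of the Child-Pugh score can themselves reach grade 4; 1.4.1 reports grade 4 hyperbilirubinemia and encephalopathy after radiation. A fatal case suspected to be related meets the second trigger.
- *Month 6 is the only review before accrual ends.* That needs a DSMC clock aligned to the first participant, the minimum frequency, and exactly 12 months of accrual. Section 10.1 permits more frequent review. Reviews at months 3 and 9 would see 0 and about 7 complete windows.
- *An excess would come to light only after all 15 are irradiated.* Adverse events and Child-Pugh score are assessed at each visit (6.1.6). A complete window is needed to call someone a non-case; a case is visible when it occurs.

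It is also fair that 4.8 and 10.1 allow suspension without a grade floor, that 10.1 defers to an institutional monitoring plan not included here, and that this is a pilot without a hypothesis test. The gap is therefore one of pre-specification; discretionary mechanisms do exist.

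The remedy has limits too. At a true 40% it triggers in time only about a quarter of the time. It needs no attribution, so a background-driven rate of 50% would prompt a review about 46% of the time. If the visit after the 6-week one falls 3 months later, near 4.5 months, confirmation lags and the 46% falls to roughly 34-40%.

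What remains is that no section says what RILD count leads to action.

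**Conclusion.** The point holds in this form: 8.7 has no RILD count or rate criterion, the discretionary provisions supply no threshold, and Child-Pugh-defined RILD alone does not pause accrual. That conclusion rests on the text and needs no assumption. The figure of about 3 complete windows (2 to 4) at month 6 rests on uniform accrual and a DSMC calendar that starts with the first participant. The trigger probabilities rest on evenly spaced starts, complete windows only, and the illustrative 30% reference and prior. This is a worthwhile, inexpensive improvement to a safety rule. It does not show that the trial lacks safety oversight.

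**What to change.** Add to 8.7 a pre-stated boundary for the number of RILD cases that pauses accrual for an unscheduled DSMC review. Count each case when it occurs. The DSMC sets the reference rate; the boundary above is one example. No participant's treatment changes.

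State how the denominator is formed. The probabilities above count complete windows only. Entering cases earlier while non-cases wait for their window would raise both timely and unnecessary triggers, so the final table should be recomputed for the chosen rule. Say in 8.7 that the count requires no attribution and that the DSMC weighs natural decline at the review.

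Cost: one table and a running count from data already collected. The price is about a 9% chance of an unnecessary review at a true 30%, more if the background rate of decompensation is higher, and limited sensitivity at 40%.

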## 9. STATISTICAL CONSIDERATIONS

Refer to Section 3.1, *Description of the Study Design* for a detailed description of the study design and endpoints.

### 9.1 ANALYSIS POPULATIONS

Safety analysis set: All participants will be evaluable for toxicity from the time of their first fraction of SBRT.

Efficacy analysis set: The analysis population to assess transplantation eligibility (i.e., Milan criteria) and efficacy endpoints (e.g., localized control rate, intrahepatic progression, extrahepatic progression and overall survival), will include only participants who have received at least 85% of the prescribed SBRT dose (i.e., 85% Level 0 = 34 Gy; 85% Level -1 = 30 Gy; 85% Level -2 = 25.5 Gy).

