#### 3.2 STUDY ENDPOINTS

##### 3.2.1 PRIMARY ENDPOINT

Endpoint	Start	End
Proportion of participants who are transplanted or with localized disease control that meets Milan criteria (Section 7.5) within 1 year	Start of SBRT	Time of progression, or transplantation, or 1-years after last SBRT dose, whichever occurs first

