#### 5.2 DOSING DELAYS AND MODIFICATIONS

SBRT will be delivered in a total of 5 fractions over two weeks, with treatments delivered every other day between Monday and Friday. SBRT will not occur on Saturdays, Sundays or holidays. There should be no more than a 14 day interruption between the planned administration of each fraction. Dosing interruptions lasting longer than 14 days between each fraction, for any reason, are considered an unacceptable and participants will be removed from

study and replaced with another participant. Participants removed from study will be treated per institutional standards or offered participation in another clinical trial if one is available. All dosing interruptions should be recorded in CRF.

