#### 9.2.2 ANALYSIS OF PRIMARY ENDPOINT

Using the efficacy analysis set, the proportion of transplant eligible participants at 1 year (per Milan criteria, Section 7.5) will be measured from time of first SBRT dose, reported with 95% exact confidence interval (CI).

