#### 9.2.3 ANALYSIS OF THE SECONDARY ENDPOINTS

Using the efficacy analysis set, the estimate of local control rate, intrahepatic progression free survival, and overall survival, will be plotted using Kaplan-Meier curve and reported with median survival and 95% CI if available. Using the same efficacy analysis set, the proportion of participants that proceed to transplantation, will be measured and reported with 95% CI.

Non-classic RILD, liver toxicity defined as a  $\geq 2$  increase in CP score (**Appendix A**), and liver toxicity per CTCAE v5.0, will be estimated along with an exact CI using the safety analysis set.

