### **9.3 SAMPLE SIZE, POWER, ACCRUAL RATE AND STUDY DURATION**

#### **9.3.1 SAMPLE SIZE AND POWER**

The primary goal of this pilot study is to help identify unforeseen problems with a subsequent larger-scale clinical trial. We predict that there is a 20% probability that a particular patient's treatment plan will fail to meet all dosimetric constraints, most notably the 700 cc critical volume constraint for the liver minus GTV since many cirrhotic patients have small total liver volumes, rendering them ineligible for SBRT. A sample size of 15 patients will ensure that we will encounter at least one incidence of SBRT ineligibility at a 95% CI.

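### The primary proportion, the transplant proportion and overall survival count only participants who complete SBRT, so those who start and stop early leave the denominator of a feasibility estimate

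*Combined protocol and SAP*

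**What the plan says.** Section 9.1 defines two sets. For safety, "All participants will be evaluable for toxicity from the time of their first fraction of SBRT". For efficacy, expressly including transplant eligibility and overall survival (OS), the set "will include only participants who have received at least 85% of the prescribed SBRT dose", with cut-offs printed as 34, 30 and 25.5 Gy for the 40, 35 and 30 Gy levels.

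Section 9.2.2 specifies the primary analysis as follows: "Using the efficacy analysis set, the proportion of transplant eligible participants at 1 year", timed from the first SBRT dose, with an exact 95% interval. Section 9.2.3 uses the same set for OS and adds: "Using the same efficacy analysis set, the proportion of participants that proceed to transplantation". Section 3.2.1 words the primary endpoint as "Proportion of participants who are transplanted or with localized disease control that meets Milan criteria" within a year and gives the start of SBRT as its starting point.

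Under Section 5.2, a participant with more than 14 days between fractions is removed from "study and replaced with another participant", and "Participants removed from study will be treated per institutional standards or offered participation in another clinical trial if one is available". Section 4.6 lists toxicity and progression among the reasons for stopping treatment. Section 9.3.1 says the pilot's main goal is to find unforeseen problems before a larger trial, and justifies the size thus: "A sample size of 15 patients will ensure that we will encounter at least one incidence of SBRT ineligibility".

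**The concern.** The endpoint clock starts at the first fraction, but membership of the denominator is settled only at the fifth. Whatever happens in between (toxicity, deterioration, death, a long interruption) takes the participant out of the headline estimate instead of counting in it. In patients with Child-Pugh B8 or worse cirrhosis, not finishing five fractions is part of the answer to whether SBRT is a feasible bridge. Section 1.3 also wants the estimate compared with historical controls, and the 20-30% progression figure in Section 1.1 refers to listed patients, not to patients who completed a treatment.

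Replacement under Section 5.2 adds to this, because the reported sample size can look intact after treated participants have gone. OS has the same feature: Section 7.3.5 starts it once 85% of the dose has been given, so a death between fractions falls outside OS altogether.

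**Working it through.** **1. The plan's own figures.** The cut-offs are 0.85 × 40 = 34 Gy, 0.85 × 35 = 29.75 Gy (printed as 30) and 0.85 × 30 = 25.5 Gy. The sample size uses a 20% chance of planning failure (Section 9.3.1): n = ln(1 − 0.95)/ln(1 − 0.20) = 13.43, rounded up to 14. The plan's 15 gives 1 − 0.8^15 = 0.965, so 15 is adequate. It does not depend on the analysis set.

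**2. What 85% means.** Sections 5.1.3 and Table 2 give five fractions. Equal fractions are not stated in words, but the per-fraction values in Table 3 are totals divided by 5.

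| Level (Gy) | 4 of 5 fractions | Share | 85% cut | Meets cut? |
|---|---|---|---|---|
| 40 | 32 Gy | 80% | 34 Gy | No |
| 35 | 28 Gy | 80% | 29.75 Gy | No |
| 30 | 24 Gy | 80% | 25.5 Gy | No |

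Only the fifth fraction crosses the cut. The rounding of 29.75 to 30 changes no classification. The exception in Section 7.1, which keeps participants interrupted for more than 14 days after reaching 85%, cannot arise with five equal fractions.

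**3. Chance that someone is excluded.** The documents give no non-completion rate, so q is assumed: P(at least one) = 1 − (1 − q)^n. They also do not say whether planning failures count toward the 15, so both n = 15 and n = 15 × 0.8 = 12 starters are shown.

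| q | 15 start | 12 start |
|---|---|---|
| 5% | 54% | 46% |
| 10% | 79% | 72% |
| 20% | 96% | 93% |

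At q = 2% and 15 starters it is 26%.

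**4. Size of the shift.** These are assumed outcomes with Clopper-Pearson 95% intervals. The all-treated column is ordered by how many non-completers succeed (0, 1, 2). Differences are in percentage points, from unrounded values.

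| Starters | Non-completers | Reported | All treated | Reported minus all treated |
|---|---|---|---|---|
| 15 | 1 | 10/14 = 71.4% (41.9-91.6) | 10/15 = 66.7% (38.4-88.2); 11/15 = 73.3% (44.9-92.2) | +4.8; −1.9 |
| 15 | 2 | 9/13 = 69.2% (38.6-90.9) | 9/15 = 60.0% (32.3-83.7); 10/15 = 66.7% (38.4-88.2); 11/15 = 73.3% (44.9-92.2) | +9.2; +2.6; −4.1 |
| 12 | 1 | 8/11 = 72.7% (39.0-94.0) | 8/12 = 66.7% (34.9-90.1); 9/12 = 75.0% (42.8-94.5) | +6.1; −2.3 |
| 12 | 2 | 7/10 = 70.0% (34.8-93.3) | 7/12 = 58.3% (27.7-84.8); 8/12 = 66.7% (34.9-90.1); 9/12 = 75.0% (42.8-94.5) | +11.7; +3.3; −5.0 |
| 17 | 2, both replaced | 10/15 = 66.7% (38.4-88.2) | 10/17 = 58.8% (32.9-81.6); 11/17 = 64.7% (38.3-85.8); 12/17 = 70.6% (44.0-89.7) | +7.8; +2.0; −3.9 |

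Three non-completers among 15, the expected number at q = 20%, give a wider spread: 8/12 = 66.7% reported, against 8/15 = 53.3% (+13.3) if all three fail or 11/15 = 73.3% (−6.7) if all three succeed.

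**5. Can the all-treated figure be recovered afterwards?** Section 6.5 times visits from completion of SBRT. Section 6.6 requires one evaluation within 30 days of early stopping. Section 5.2 takes interrupted participants off study. Section 9.4 imputes nothing but states each analysis's sample size and reasons for exclusion. A reader could therefore bound the all-treated proportion but not recover it.

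**The case against.** The strongest reply concerns the direction of bias. Milan status (Section 7.5) depends on tumour size, number, vessel involvement and spread, not on liver function, so stopping for toxicity is not in itself a failure. Progression is unlikely to be seen during a course of about 10 days in which the only scheduled imaging is cone-beam CT. This stands as a caution: upward bias is the likelier direction, because stopping for toxicity, progression or death should tend to go with later failure, but it is not assured.

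The shifts above are also selected examples and not bounds. They lie within very wide intervals, no test or threshold depends on them, and they are zero if everyone completes. All of that is true. But wide intervals describe random error and do not justify an avoidable selection.

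On follow-up, early stopping is not an off-study criterion in Section 4.7, Section 4.6 lets willing participants continue with visits, and Section 6.5 ends follow-up 2 years after the last SBRT dose, which also fits non-completers. The clear gap is therefore the group removed under Section 5.2; for other non-completers, one-year status is merely not clearly secured.

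Finally, the synopsis words the endpoint as eligibility 1 year following SBRT, and a minimum-dose evaluable set is a familiar device. For in-field local control it is defensible. The synopsis wording does not, however, limit the denominator to completers.

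**Conclusion.** The concern holds for three endpoints: the primary proportion, the proportion transplanted and OS. As planned, each describes participants who finished five fractions, while the trial asks about patients who start SBRT as a bridge. With one or two non-completers, the illustrated shift in the primary proportion runs from about −5 to +12 points, and three would widen it. The corresponding intervals are about 46 to 59 points wide (12/17 and 7/10 in the table). The conclusion rests on equal fractions; its size rests on an assumed non-completion rate and assumed outcomes, since the documents give neither. It should be fixed, but it does not invalidate the trial or alter its sample size. Planning failures, the barrier named in Section 9.3.1, never start SBRT and are in neither set, so changing the denominator does not capture them.

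**What to change.** 1. In Sections 9.1, 9.2.2 and 9.2.3, make everyone who received at least one fraction (the existing safety set) the primary denominator for the primary proportion, the transplant proportion and OS. Keep the 85% set as supportive. Local control may stay on the 85% set, with the all-treated result alongside.
2. Keep replaced participants in the denominator. Report the numbers of non-completers and replacements, with reasons. Report planning failures separately; Section 6.3.1 already records the reason for screen failure.
3. Amend Sections 5.2, 6.5 and 6.6 so that transplant, Milan and survival status is still collected for non-completers and those removed under 5.2, unless consent is withdrawn. Show the primary proportion with non-completers of unknown status counted as all failures and as all successes.
4. Reconcile the OS origin in Section 7.3.5 with the first-dose start that Section 3.2.2 appears to give, and the interruption exception in Section 7.1 with Section 5.2. The treatment rule in 5.2 is not itself in question.

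The cost is SAP wording, a small protocol amendment on follow-up, and continued contact with a few participants, whose later outcomes may also reflect other treatment. The headline proportion may be lower.
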